The study uses a wait-list **experimental design** to estimate treatment impacts, with 30 Ohio classrooms assigned to the treatment condition and 20 to the control condition. All remaining 40 classrooms will be recruited by our partners at external sites and serve control condition classrooms. Within each classroom, the focal participants are 30 children with LI, one selected per classroom using a priori exclusionary and inclusionary criteria. The wait-list design allows eligible children with LI in control classrooms to receive treatment in the spring semester; this also allows for ongoing evaluation of changes in socialization processes in treatment classrooms through spring. Study methods with OSU classrooms use a sequential cohort design, with 15 classrooms participating in each of two consecutive years to disperse study activities over a 24-month period. Classrooms will be recruited via our extensive network of affiliated preschool programs across the state of Ohio, with eligible classrooms utilizing a 50/50 inclusive service delivery model (50% of children with disabilities). In the fall of each year, once all 15 classrooms are recruited, simple random assignment will be used to allocate 10 classrooms to the treatment group and 5 to the control group, with the latter implementing intervention in spring per the wait-list design. In addition, our colleagues at the University of Kansas, are employing similar observation methods. We will thus incorporate 20 classrooms (University of Kansas) to serve as control condition classrooms, allowing for a more robust sample of natural conditions in preschool classrooms across contexts.

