#### **g. Data Analysis**

Aim 1 investigates the effects of peer-mediated PRT on the peer interactions and social status (indicated by individual centrality) within the classroom social network for children with LI. We assess this aim based on 6 to 24 repeated measurements for each outcome variable using multilevel growth models (Raudenbush & Bryk, 2002) to investigate changes in key outcomes over the school year and to accommodate the wait-list experimental design. Longitudinal measurements will be nested within participants and predicted by the time of measurement as well as time-specific intervention status. We include interaction terms between time of measurement and intervention status so that any accelerating or decelerating effects of intervention can be captured. In all models, we control for relevant covariates to increase precision of parameter estimates and power (Hox, Moerbeek, & Van de Schoot, 2010; Raudenbush, Martinez, & Spybrook, 2007). To assess treatment effects on peer interactions, we use the number of peer interaction, number of appropriate peer play, and duration of peer talk for the focal children as the outcome variables in the growth models. Depending on the distribution of the variables, appropriate linear or generalized linear models (e.g., Poisson) will be fitted. To examine treatment effects on social status, we compare the trajectories of individual centrality for the focal children and their classmates, controlling for classroom-level variation. Specifically, intervention effects are tested on key components of the trajectories, such as intercept, linear slope and quadratic slope (i.e., the slowing or acceleration of growth). The growth curves for different groups (treatment, wait-list control, and peer) can then be estimated. Aim 2 determines the extent to which peer-mediated PRT contributes to focal children's social, behavioral, and linguistic skills via the mediation of improved socialization experiences. For this aim, we employ multivariate latent growth models, where latent growth curves of socialization indices and child skills can be modelled simultaneously and the relationships between latent growth parameters examined. In particular, two latent slopes (fall and spring) will be specified for the socialization growth curve to capture the differential growth rate with and without intervention; intervention status will be used as a predictor of the two socialization slopes. Due to the sample size limitation, we will examine one socialization index and one skill variable at a time. We will focus on the following pathways: (a) effect of intervention on focal children's socialization experiences at fall, winter, and spring; and (b) effects of socialization experiences on child skills at fall, winter, and spring. Paths (a)\*(b) allow us to test the indirect effects of PRT on social, behavioral, and linguistic skills. To estimate the mediation effect, we use the product-of-coefficient approach (MacKinnon, Lockwood, Hoffman, West, & Sheets, 2002) with a bootstrapping procedure (Preacher & Hayes, 2004, 2008). This method does not require the assumption of normality for the sampling distribution of the product-of-coefficient. Finally, Aim 3 examines changes in classroom social network dynamics over the school year, and tests the effects of peer-mediated PRT on peer socialization at the classroom level. To address this aim,

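### Aim 1 social status: group differences in the intercept and slopes of year-long curves do not measure the PRT effect when the Ohio wait-list arm gets PRT in spring, and the status term repairs this only in part

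*Combined protocol and SAP*

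**What the plan says.** Section III.g (Data Analysis) opens Aim 1 with a general model. Growth models are chosen "to accommodate the wait-list experimental design", and repeated measures are "predicted by the time of measurement as well as time-specific intervention status". It adds: "We include interaction terms between time of measurement and intervention status".

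For social status (individual centrality) the section becomes more specific. It says "we compare the trajectories of individual centrality for the focal children and their classmates, controlling for classroom-level variation", then that "intervention effects are tested on key components of the trajectories, such as intercept, linear slope and quadratic slope", and finally "The growth curves for different groups (treatment, wait-list control, and peer) can then be estimated".

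Section III.a (Research Design) says: "The wait-list design allows eligible children with LI in control classrooms to receive treatment in the spring semester". Of the Ohio classrooms randomised each fall, it describes the control group "with the latter implementing intervention in spring per the wait-list design". It also adds external control classrooms, for which no PRT is described. Under Intervention Implementation, facilitator support lasts 12 weeks.

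The plan does not give the PRT start weeks or the position of time zero. It does not say how status is coded once the 12 weeks end, or how time-specific status enters the component tests for centrality.

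**The concern.** Both randomised Ohio arms receive PRT within one school year. If PRT works and lasts, the difference between them is zero at the start, largest in winter and closing by late spring. The intercept, linear slope and quadratic slope of a curve fitted to the whole year do not estimate that winter difference.

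If time zero is the start of the year, the intercept describes children before anyone has had PRT. A difference there between randomised arms is chance imbalance or a by-product of curve fitting, yet the plan would test it as an intervention effect. The plan describes the quadratic term as slowing or acceleration of growth, so a lasting benefit that the wait-list arm catches up with would be read as slowing growth in the treatment arm. Two analysts following the same text could report different conclusions on social status from the same data.

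**Working it through.** The plan gives no power or effect figure for Aim 1, so there is nothing to reproduce. The check asks what each component would show for a known effect.

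**Inputs.** From the plan: 12 weeks of PRT, 9 months of participation, fall PRT for treatment, spring PRT for the Ohio wait-list. Assumed: a 36-week year, time zero at its start, a true effect of 1.0 and the start weeks below (treatment/wait-list). The effect is either immediate or builds evenly over 12 weeks.

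**Fixed-group linear fit, 12-week build-up.** Let d(t) be the expected treatment minus wait-list difference, with t in fractions of the year. The least-squares slope is 12∫(t - 1/2)d(t)dt, and the intercept is mean(d) - slope/2.
- Starts 4/20, maintained: d rises over weeks 4-16, is flat to week 20 and falls to week 32. Its area is 6 + 4 + 6 = 16 weeks, mean 16/36 = 0.44, centred on week 18. Slope 0.00; intercept +0.44.
- Starts 6/22, maintained: same shape centred on week 20. Slope = 12 × 0.444 × (20/36 - 1/2) = +0.30; intercept = 0.44 - 0.15 = +0.30.
- Starts 4/20, effect lost when support ends: two triangles of area 6, centred on weeks 12 and 28. Slope = 12 × (6/36) × (12 - 28)/36 = -0.89; intercept = 0 + 0.44 = +0.44.

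**Fixed-group linear fit, immediate lasting effect.** With starts at fractions t1 and t2 of the year, slope = 6[t1(1 - t1) - t2(1 - t2)]. For 0.25 and 0.75 this is 0.00. For 0.20 and 0.60 it is 6(0.16 - 0.24) = -0.48.

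**Fixed-group quadratic fit.** At 4/20, build-up, maintained: intercept -0.32, linear +4.61, quadratic -4.61. The fitted mid-year difference is -0.32 + 4.61/2 - 4.61/4 = 0.83. The signal is visible, but no single coefficient is the effect. The intercept was negative in every maintained build-up case tried. With an immediate effect and early starts it can stay positive (+0.18 at 4/20 with 12 visits).

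**Simulation of the fixed-group reading.** 100 runs, 20 and 10 children, 12 visits, immediate effect 0.50, SDs 0.7, starts 9/27. Rejection was 3% for the group difference in linear slope, 13% for the intercept and 72% for the quadratic term. The time-specific status term gave 99%.

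**Does the status term cure it?** That simulation used an immediate effect with status left on. Noise-free fits (12 visits, 20 and 10 classrooms, arm intercepts, starts 4/20, 6/22, 8/20 and 9/27, maintained effect of 1.0) show how far the result carries.

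Status coefficient without the interaction, using linear, quadratic or per-visit time:
- immediate, status stays on: 1.00
- immediate, status on only during PRT: 0.48 to 0.53
- build-up, status stays on: 0.13 to 0.48
- build-up, status on only during PRT: -0.05 to 0.07

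With the plan's interaction with time of measurement, under build-up, the fitted arm difference at the last visit before wait-list start is:
- status stays on: about 0.65 to 0.95 in most settings. Linear time gives 0.65 to 0.77. Quadratic time gives 0.83 to 0.91 for three of the start pairs and 1.05 for 9/27. Per-visit time gives 0.97 to 1.15.
- status on only during PRT: about 0.40 to 0.50. At 4/20 the whole 0.42 is arm intercept, because status is off in both arms at that visit.

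**The case against.** The strongest reply is that section III.g already specifies a crossover-aware model. Status varies over time and interacts with time, so the component sentence can mean that status shifts level and slope, not that fixed arms are compared. Other parts of the plan fit that reading: Aim 2 has separate fall and spring slopes, and Aim 3 compares the intervention and control periods. This carries weight. It limits the point to social status; peer interactions, appropriate peer play and peer talk come under the general model. It does not remove the point, because the component tests are followed by curves for fixed groups, status after 12 weeks is uncoded, and the interaction uses time of measurement rather than time since PRT start.

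Three further replies stand in part:
- The exact 0.00 slope needs a difference curve centred on mid-year. With build-up and a maintained effect, other starts give slopes that favour treatment, such as +0.30 (6/22) and +0.59 (8/24).
- The plan names a quadratic term, and much of the signal would appear there.
- External controls have no PRT described. If they are pooled, one third of controls are wait-list under either set of counts in section III.a (20 of 60, or 10 of 30), and the 4/20 maintained slope difference becomes +0.77. That changes the slope by adding a non-randomised comparison.

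The remedy is also partly a choice: a pre-crossover contrast sets aside spring data that the plan means to use.

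**Conclusion.** The point holds for the social-status outcome. If the tested components are fixed-group components, none of them is the PRT effect. The linear-slope difference can be near zero, attenuated or reversed, part of the effect leaks into the start-of-year intercept, and a lasting effect that the wait-list arm matches in spring shows as a negative quadratic. The status term with its interaction is exact only for an immediate effect with status left on. Under a 12-week build-up it mostly understates the winter difference, at about 0.4 to 0.95 of a true 1.0, and in some settings slightly overshoots.

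A reader might infer that all of Aim 1 is invalid, that a real effect always gives no slope difference, or that it would go undetected. The documents do not support this. The general model includes time-varying status, a zero slope needs particular timings, and the quadratic term would often pick up a signal. What is shown is that the estimated quantity is ambiguous and that its natural readings can mislead.

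All magnitudes rest on assumed start weeks, year length, visit spacing, effect shapes and, for the simulation, SDs. The documents give none of these except the 9-month period and an 8-16 (elsewhere 6-24) visit count.

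**What to change.** For social status:
- State that group differences in year-long intercept, linear and quadratic terms are not interpreted as intervention effects.
- Model time in segments tied to each classroom's actual PRT start and end, or as time since PRT start, and define time zero.
- Constrain the randomised Ohio arms to a common start-of-year mean.
- Name one main effect: treatment minus wait-list focal-child centrality at the last visit before wait-list classrooms start.
- Keep the time-specific-status model as a supporting analysis that uses the spring crossover data, with the coding of status after the 12 weeks stated.
- Report wait-list uptake, treatment-arm maintenance and comparisons with the non-randomised external controls separately.

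The cost is SAP wording and model code; no data collection changes. The downside is that the main contrast uses less of the spring data, which the supporting model partly offsets.

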### **b. Sample**

This study examines the socialization experiences of preschool children with LI inclusive classrooms and the entire classroom social network. Thus, we seek to consent all children in each classroom as participants in this study. For children who are not focal children or peers assisting with the intervention, we will seek caregiver consent to observe their children in the classroom and for caregivers to complete a simple questionnaire about their children. We typically are able to actively or passively consent 90% of children in a classroom.

Focal children (n = 30). We describe inclusionary and exclusionary criteria for the 30 focal children with LI. First, we identify all children's positions (n = 495) within the classroom social network using a teacher matrix conducted in fall of the academic year; from this network we calculate a child-level social network index (i.e., individual degree centrality; lower scores are characteristic of social exclusion (Justice, Chen, et al., 2019)). Second, teachers simultaneously complete the Developmental Pragmatic Profile (DPP) (Wiig, Secord, & Semel, 2004) for each child in the classroom. This is a 26-item psychometrically sound checklist assessing children's pragmatic skills (e.g., conversational abilities, giving information), and DPP scores have strong classification accuracy in differentiating children with LI from non-affected classmates (Justice, Ahn, & Logan, 2019). Third, teachers also use a checklist to identify children with LI in each classroom per four criteria: the child (1) is on the caseload of a speech-language pathologist, (2) has no known additional diagnoses causal of LI, such as ASD, (3) primarily communicates in English, and (4) is greater or equal than 42 months of age. Finally, among the children with LI, we select the target child based on the lowest centrality scored weighted by DPP score, so that focal children represent the most socially isolated children with the poorest social-pragmatic communication skills.

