Main Study: Focal children in OSU-based treatment condition classrooms will receive peer-mediated PRT per procedures detailed by Brock et al (Brock, Dueker, & Barczak, 2018). PRT procedures are facilitated by a classroom facilitator—a classroom teacher or teaching assistant—who will receive ongoing training and support from research staff. Focal children receive peer-mediated pivotal response treatment. With carefully identified classroom peers, facilitators hold four 15-minute training sessions with the peer group, each developing 1 of 4 strategies to use to engage with the target child. The facilitator explicitly identifies the focal child ('buddy') and asks the children to use four strategies to play with the child during center time: a) offer your buddy some play options; b) show and talk about how to play with your buddy; c) compliment your buddy; and d) show your buddy how to take turns. After the trainings are complete, the facilitator provides ongoing support to peers during center time to implement the strategies by regularly encouraging them and supporting them to use the strategies, praising them when they use the strategies well, and reviewing their interactions with the focal child at the end of center time. Facilitators provide this support during center time at least 3 times weekly for a 12-week period.

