### **d. Measures and Instrumentation**

**Researcher observations.** Researcher observations of peer social interactions are adapted from a validated observation protocol (Schaefer, Light, Fabes, Hanish, & Martin, 2010).

Pilot Study: Using trained, reliable observers blind to study hypotheses and classroom study condition, a ~40-min observation session will be conducted in each classroom once per week during weeks 2-6 of the pilot. The observer will observe the classroom during center time and use the list of peer and focal children to structure four partial interval observation cycles; in each cycle, the observer observes each child for 15 s followed by 15 s recording and then moves to the next child. At the end of one cycle, the observer takes a 5-min break. When observed, each child is recorded for any interaction partners (up to five) based on presence of a verbal or physical exchange or parallel play in the same activity during the 15-s observation. Reliability estimates will be assessed for 10% of cycles via double-coding. Based on researcher

observations, a social network will be created for each classroom per observation window. It will be stored in a symmetric square matrix, where the rows and columns represent the classroom roster and each cell value refers to the frequency at which the pair of children play with each other.

Main Study: Using trained, reliable observers blind to study hypotheses and classroom study condition, a ~40-min observation session will be conducted in each classroom 8-16 times over the academic year. The observer will observe the classroom during center time and use a randomized list of children to structure four partial interval observation cycles; in each cycle, the observer observes each child for 15 s followed by 15 s recording and then moves to the next child. At the end of one cycle, the observer takes a 5-min break. When observed, each child is recorded for any interaction partners (up to five) based on presence of a verbal or physical exchange or parallel play in the same activity during the 15-s observation. Reliability estimates will be assessed for 10% of cycles via double-coding. Based on researcher observations, a social network will be created for each classroom per observation window. It will be stored in a symmetric square matrix, where the rows and columns represent the classroom roster and each cell value refers to the frequency at which the pair of children play with each other.

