For the proposed study, researcher observations are executed on days these location recordings occur, so that we can not only triangulate the social network data, but also validate that social networks based on location tracking validly represent authentic forms of peer socialization. Based on each social network generated from either researcher observation or location tracking across the 8-16 timepoints, the social status of each child in the classroom network will be represented by two types of individual centrality indices: degree centrality (i.e., the amount of social interactions directly associated with a child) and eigenvector centrality (i.e., the amount of social interactions directly associated with a child and indirectly associated with the child through their peers, e.g., “friends’ friends”). Classroom network density is also calculated to represent the average interaction intensity in the classroom, with higher values representing a more closely connected classroom network.

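### The classmate comparator for social status is itself exposed to treatment: the one 'peer' group is not split by arm and does not separate the trained buddies

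*Combined protocol and SAP*

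**What the plan says.** For social status, III.g Data Analysis states that "we compare the trajectories of individual centrality for the focal children and their classmates, controlling for classroom-level variation". It then names three sets of curves: "The growth curves for different groups (treatment, wait-list control, and peer) can then be estimated". Focal children are divided by arm; peers are not, and the term is not defined there. The growth models are described as having outcomes "predicted by the time of measurement as well as time-specific intervention status", without saying whether that status is coded for classmates or only for focal children.

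The intervention works through classmates. In III.c, Intervention Implementation (Main Study): "With carefully identified classroom peers, facilitators hold four 15-minute training sessions with the peer group". These children are then supported during center time at least 3 times weekly for 12 weeks. III.b Sample treats them as a distinct group for consent: "For children who are not focal children or peers assisting with the intervention, we will seek caregiver consent". The analysis section does not carry that distinction over.

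In III.d, the network from researcher observations is described thus: "It will be stored in a symmetric square matrix, where the rows and columns represent the classroom roster". The index is "degree centrality (i.e., the amount of social interactions directly associated with a child", whoever the partner is.

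**The concern.** A comparator should not move because of the treatment it is used to judge. Here some classmates are asked to play with the focal child, and a symmetric network credits each such contact to both children. The classmates' curve can therefore shift when PRT starts.

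Two things are at stake. First, a focal-minus-classmate contrast no longer equals the focal child's own gain. Second, if buddies give up other playmates to spend time with the focal child, trained buddies and untrained classmates move in opposite directions. One averaged peer curve would hide this. Goal 3 asks about broader effects on classroom network dynamics, so such a redistribution is of interest to the study.

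**Working it through.** The documents give no figure for this shift, so there is nothing to reproduce. The check uses the arithmetic of degree in a symmetric matrix.

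**Inputs from the documents**
- Children per room, n. III.b gives 495 children for 30 focal children, one per room: 495/30 = 16.5. III.a gives 900 children in 90 rooms: 900/90 = 10.0. The same sentence also gives 770: 770/90 = 8.6. These do not agree, so all three are used.
- Allocation. III.a gives 10:5 Ohio rooms per year (2:1), and elsewhere 30:20 Ohio rooms plus 40 external control rooms.

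**Assumptions (not in the documents)**
- k, the number of trained buddies per room: 1 to 3.
- f, the fraction of new focal-buddy contacts that replace contacts between a buddy and an untrained classmate: 0 to 1.

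**Formulas.** Let the focal child's degree rise by D through contacts with k buddies.
- The buddies gain D in total. Each displaced contact lowers two classmates' degrees, so the classmates' total changes by D − 2fD.
- Mean shift of all classmates: D(1 − 2f)/(n − 1).
- Each buddy: D(1 − f)/k.
- Each untrained classmate: −fD/(n − 1 − k).
- Within-room focal-minus-classmate contrast: D[1 − (1 − 2f)/(n − 1)].
- A curve pooled over arms moves by the treated share times the mean shift.

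**Results, in units of D**

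| n | Classmate mean, f = 0 | Contrast, f = 0 | Pooled 2:1, f = 0 | Untrained classmate, f = 0.5, k = 1 to 3 | Contrast, f = 1 |
|---|---|---|---|---|---|
| 16.5 | 1/15.5 = 0.065 | 0.935 | 0.043 | −0.034 to −0.040 | 1.065 |
| 10.0 | 1/9 = 0.111 | 0.889 | 0.074 | −0.062 to −0.083 | 1.111 |
| 8.6 | 1/7.56 = 0.132 | 0.868 | 0.088 | −0.076 to −0.110 | 1.132 |

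- With f = 0, each buddy rises by 1.00D, 0.50D or 0.33D for k = 1, 2 or 3.
- With f = 0.5, the classmates' mean shift is exactly 0. Even so, each buddy gains 0.50D, 0.25D or 0.17D while untrained classmates lose.
- With f = 1, buddies' totals do not change and the classmates' mean falls by 0.065D to 0.132D. Contacts gained equal contacts lost, so network density does not move either.
- The pooled figures apply only while one arm is treated. At 30:20 the pooled shift is 0.039D to 0.079D. With external controls included (30 of 90 rooms) it is 0.022D to 0.044D.

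A simulated 16-child matrix with 2 buddies and a focal gain of 6 agreed: buddies rose by 3 each, and the classmates' mean rose by 1/15 of the focal gain. Eigenvector centrality moved similarly (focal +0.041, buddies about +0.02 each, untrained classmates −0.008 on average).

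**The case against.** The strongest reply is that the randomised comparison does not need the peer curve. Treated and wait-list focal children have their own curves, and their difference is untouched. A single curve pooled over arms also cancels from a between-arm comparison: (treatment − peer) − (wait-list − peer) = treatment − wait-list. Both points stand. The shift enters a between-arm comparison of focal-minus-classmate differences only if each arm has its own classmate curve. The other Aim 1 outcomes (peer interaction, appropriate peer play, peer talk) are modelled for focal children alone.

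A second reply is that the intervention-status term and the control for classroom-level variation may already deal with this. That stands only in part. Coded for focal children only, the status term labels trained buddies untreated; coded by classroom, it averages them with untrained classmates. Neither separates the roles. A classroom-level term does not remove a shift that differs between children in one room and begins with treatment.

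Third, goal 3 concerns the classroom level and does not promise results for untrained classmates. That is fair: a split by role adds information there and does not repair a broken Aim 3 analysis.

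A reader might infer more than the text supports:
- That the plan states peers are pooled over arms. This is the natural reading of a three-group list, but it is not written.
- That buddies' degree must rise. Only the focal-buddy contact is certain to count for both children; a buddy's total rises only if displacement is incomplete.
- That the effect is always understated. The direction depends on displacement, on which the documents are silent.

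**Conclusion.** The point holds for the focal-versus-classmate comparison of centrality. That comparator includes children the intervention trains, and the plan neither excludes nor separates them.

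With no displacement, the within-room contrast is understated by about 6% to 13% of the focal gain, depending on which class size is right. At half displacement the mean bias is nil, but the peer curve hides gains by buddies and losses by untrained classmates. Beyond half, the contrast is overstated, by up to the same 6% to 13%. A curve pooled over Ohio arms at 2:1 moves by about 4% to 9% of the focal gain with no displacement, and by less if external controls are included. The range of f and the number of buddies are assumptions.

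The documents do not support reading this as a bias in the treated versus wait-list focal contrast. They do support the narrower conclusion that the social-status analysis needs its groups defined by role, arm and period.

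**What to change.** In III.g Data Analysis:

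1. Name the contrast of treated with wait-list focal children, before wait-list classrooms start PRT, as the treatment effect on social status.
2. Replace the single peer curve with separate groups, coded by arm and period: trained buddies; untrained classmates in rooms receiving PRT; and classmates in rooms not yet receiving it. State how intervention status is coded for each.
3. Report the focal-versus-classmate comparison with trained buddies left out of the comparator. Note that untrained classmates may still be affected: their direct shift is 0 without displacement, and about −0.03D to −0.11D at half displacement.
4. Use not-yet-exposed classmates as the unexposed reference for the pre-PRT period only. They cannot serve all year, because wait-list rooms receive PRT in spring. As the sole reference they would also give up the within-room comparison and, by the 10:5 figure, rest on 5 Ohio wait-list rooms per year.

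Optionally, have each Ohio teacher list would-be buddies before assignment, so that trained buddies have a randomised counterpart. Teachers already complete a fall matrix and checklist, so the added burden is small, but the list cannot be recovered afterwards.

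The coding needs no new outcome data. The cost is more group terms and smaller groups, so each classmate curve is less precise.
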